#### **8.3.2 Method of detecting AEs and SAEs**

Care will be taken not to introduce bias when detecting AEs and/or SAEs. Open-ended and non-leading verbal questioning of the study participant is the preferred method to inquire about AE occurrences.

#### **8.3.3 Follow-up of AEs and SAEs**

After the initial AE/SAE report, the Investigator is required to proactively follow each study participant at subsequent visits/contacts. All SAEs, [and non-serious AEs of special interest (as defined in Section 8.3.6), will be followed until resolution, stabilization, the Investigator determines that it is no longer clinically significant, the event is otherwise explained, or the study

participant is lost to follow up (as defined in Section 7.3). Further information on follow-up procedures is given in Appendix 3 (Section 10.3).

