### **8.3 Adverse events and serious adverse events**

The definitions of device-related safety events, (adverse device effects [ADEs] and serious adverse device effects [SADEs]), can be found in Appendix 7. Device deficiencies are addressed in Appendix 7 (Section 10.7).

Adverse events will be reported by the study participant.

The Investigator and any designees are responsible for detecting, documenting, and recording events that meet the definition of an AE or SAE and remain responsible for following up AEs that are serious, considered related to the study treatment or study procedures, or that caused the study participant to discontinue the study (see Section 7).

Confirmed and suspected cases of SARS-CoV-2 infection will be recorded as AEs (or SAE, as required).

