### Follow-up of AEs and SAEs

- The Investigator is obligated to perform or arrange for the conduct of supplemental measurements and/or evaluations as medically indicated or as requested by UCB to elucidate the nature and/or causality of the AE or SAE as fully as possible. This may include additional laboratory tests or investigations, histopathological examinations, or consultation with other health care professionals.
- An AE should be followed until it has resolved, has a stable sequelae, the Investigator determines that it is no longer clinically significant, or the study participant is lost to follow up. This follow-up requirement applies to AEs, SAEs, and AEs of special interest.
- If a study participant dies during participation in the study or during a recognized follow-up period, the Investigator will provide UCB with a copy of any post-mortem findings including histopathology.
- New or updated information will be recorded in the originally completed eCRF.
- The Investigator will submit any updated SAE data to the UCB within 24 hours of receipt of the information.

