**Table 4-1: Calculation rules for duration (days) of AEs (applicable also to ADEs)**

Data Availability	Onset Date/Time	Outcome Date/Time	Calculation Rules
End day and time missing	D1/T1	--/--	For ongoing AE duration = > Discharge day – D1 d For resolved AE duration = < Discharge day – D1 d Where Discharge Day refers to the date of the SFU visit or date of discontinuation.  For any AEs with known start date/time after the date of discontinuation, the date of last contact will be used as the discharge day.
Start and end date missing	--/--	--/--	For ongoing AE duration = > Discharge day – D0 d For resolved AE duration = < Discharge day – D0 d Where Discharge Day refers to the date of the Safety Follow-Up visit or date of discontinuation. For a participant in the FAS, D0 is the date of dosing and for screen failures, D0 = the screening visit date.

ADE=Adverse Device Effect; AE = Adverse Event; FAS=Full Analysis Set

#### 4.2.5 Impact Of COVID 19

The FDA and EMA (see REFERENCES) have provided guidance to help assure the safety of study participants, maintaining compliance with good clinical practice (GCP), and minimizing risks to study integrity during the COVID-19 pandemic. At the time of writing, the impact of the pandemic is still evolving and regulators continue to clarify their position. One of the recommendations is a risk assessment of the impact of COVID-19 on study integrity and interpretability of potential study results. In particular, the major statistical principles that need to be considered when considering the impact of COVID-19 on studies and how to handle missing or delayed assessments resulting from the pandemic. The impact of the COVID-19 pandemic, at the visit level, will be assessed by data collected on a specific COVID-19 impact CRF. Drop outs due to COVID-19 will be handled in the same way as drop out for other reasons. Should one of the ongoing reviews of COVID-19 related PDs (see Section 3.4) suggest that the impact of COVID-19 is more significant than expected e.g. in the case of a second wave, the SAP may be updated to include details of strategies to handle missing data and/or sensitivity analyses.

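### Protocol Sections 8.3, 8.3.3 and 10.3.3 give three different scopes for following adverse events, none is said to govern, and one duration bound in SAP Table 4-1 can be false as a result of follow-up after discontinuation

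*Protocol*

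**What the plan says.** Three places in the protocol state which adverse events are followed up.

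- Section 8.3 holds the Investigator responsible for "following up AEs that are serious, considered related to the study treatment or study procedures, or that caused the study participant to discontinue" from the study. It gives no end point.
- Section 8.3.3 opens with a general duty: "the Investigator is required to proactively follow each study participant at subsequent visits/contacts". It then lists the events followed to an end point: "All SAEs, [and non-serious AEs of special interest (as defined in Section 8.3.6), will be followed until resolution, stabilization", or until the event is no longer clinically significant, is otherwise explained, or the participant is lost to follow up. It closes with a pointer: "Further information on follow-up procedures is given in Appendix 3 (Section 10.3").
- Section 10.3.3 (Appendix 3) says: "An AE should be followed until it has resolved, has a stable sequelae, the Investigator determines that it is no longer clinically significant", or the participant is lost to follow up. It adds: "This follow-up requirement applies to AEs, SAEs, and AEs of special interest".

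Section 8.3.6 names one AE of special interest, potential Hy's Law. Section 10.3.2 also gives potential Hy's Law as an example of a serious event.

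The SAP uses the resulting dates in Table 4-1. For an AE with a known onset but no end day or time, duration is listed as greater than Discharge Day minus D1 if ongoing, and less than Discharge Day minus D1 if resolved. The table explains: "Where Discharge Day refers to the date of the SFU visit or date of discontinuation". The date of last contact replaces Discharge Day only for AEs that start after discontinuation.

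**The concern.** A site needs one answer to a simple question: is this event to be followed until it settles? For a non-serious event that is related, or that led the participant to leave, the answer depends on which section the site opens. The section whose title is about follow-up has the narrowest list. Its second category adds little, since the only AE of special interest is also offered as an example of an SAE.

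The events concerned are the ones to be expected here. Section 2.3 puts infection first among the safety concerns and describes it as mainly non-serious. Section 7.2 provides for discontinuation because of an interfering illness and for withdrawal in certain confirmed COVID-19 cases, and Section 8.3 has such cases recorded as AEs. After discontinuation, Section 7.2 only encourages a return for the Safety Follow-up Visit, so the duty to follow participants at later visits or contacts may have little to act on. At stake is whether outcome and end date are collected in the same way for all such events, and whether the listed durations are correct.

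**Working it through.** No figure in the plan needs to be reproduced. The check sets the three scopes side by side by type of event, then tests the SAP bound.

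**Coverage by event type**

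| Event | 8.3 | 8.3.3 list | 10.3.3 |
|---|---|---|---|
| Serious AE | yes | yes | yes |
| Non-serious AE of special interest | only if related or it caused discontinuation | yes | yes |
| Non-serious, related, not of special interest | yes | no | yes |
| Non-serious, caused discontinuation, not of special interest | yes | no | yes |
| Any other non-serious AE | no | no | yes |

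No two columns agree. Only the first row gives the same unconditional answer throughout. The last column covers every row, so no event type lacks a follow-up rule somewhere in the protocol.

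**End points.** Section 8.3 has none. Sections 8.3.3 and 10.3.3 overlap but are not identical: the former allows follow-up to end when the event is otherwise explained, and the latter does not.

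**Precedence.** The only link is the closing sentence of 8.3.3, which refers to Appendix 3 for procedures. It does not say that the appendix widens or overrides the list just given.

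**SAP Table 4-1, end day and time missing.** Let D1 be onset, Dd the discontinuation date used as Discharge Day, R the unrecorded date of resolution and L the date of last contact, with D1 before Dd.

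1. Ongoing AE: listed as > Dd − D1. The event lasted beyond Dd, so the bound is true, though it ignores any later contact.
2. Resolved AE with R before Dd: listed as < Dd − D1. Since R − D1 < Dd − D1, the bound is true.
3. Resolved AE with R after Dd: listed as < Dd − D1. Since R − D1 = (Dd − D1) + (R − Dd) and R − Dd > 0, the bound is false, by R − Dd days.
4. With L in place of Dd in case 3: resolution is known by last contact, so R ≤ L and R − D1 ≤ L − D1. L − D1 is a valid upper limit.

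Case 3 arises only if an event is followed after discontinuation, as 10.3.3 asks for any AE and 8.3 for related or discontinuation-causing ones. The existing last-contact rule does not reach it, because the event started before discontinuation.

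**The case against.** The strongest reply is that nothing is missing. Section 8.3.3 requires each participant to be followed at later visits and contacts, sits under a parent section that names events causing discontinuation, and points to an appendix that covers every AE. A site would have to disregard both to stop following such an event. The unmatched bracket in the 8.3.3 sentence is consistent with leftover template text, though that is an inference.

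Most of this stands. A reader might infer that 8.3.3 releases the site from following a non-serious event that led to withdrawal, or that participants who leave because of an AE have no required follow-up. The documents support neither. Section 8.3.3 omits these events from its list without exempting them, and Section 10.3.3 already covers them.

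The objection on the SAP is also largely right. An event with a recorded end date is handled by the complete-data row, and the bound for an ongoing event stays true. Table 4-1 does not alter the recorded outcome. AE duration is listed (Protocol Section 9.5.1, SAP Section 11.2), and no planned analysis uses it.

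What the objection does not remove is that three statements of one operative safety rule differ, none is given precedence, and case 3 above yields a false entry.

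**Conclusion.** The point holds as an internal contradiction about the scope of AE follow-up, with a narrow consequence in one SAP table row. It is not a missing requirement across the protocol.

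Its size is limited. The primary analysis uses AUC, AUC(0-t) and Cmax and takes nothing from AE follow-up, so the bioequivalence conclusion does not change. An event counts as treatment-emergent by its onset or worsening relative to dosing, and Section 8.3.1 has all AEs collected whatever the follow-up scope, so TEAE counts do not change either. What can vary is how completely outcome and end date are obtained for non-serious events unresolved at discontinuation or at the last visit. How many there will be cannot be derived from the documents.

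The SAP part assumes three things together: the event began before discontinuation, it is known to have resolved afterwards on an unrecorded day, and the discontinuation date serves as Discharge Day. If the participant returns for the Safety Follow-up Visit and that date is used, the bound holds for any event resolved before that visit. The table does not say which date applies to such a participant.

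**What to change.** Reconcile Protocol Sections 8.3, 8.3.3 and 10.3.3 to one stated scope and one stated end point for AE follow-up, or state which section governs. The choice of scope is the sponsor's, and this review takes no position on it. Clear the stray bracket in 8.3.3 in the same edit.

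In the SAP Table 4-1 row for a missing end day and time, extend the date-of-last-contact rule to AEs that began before discontinuation and were followed after it.

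The drafting cost is a few sentences in the protocol and one table row in the SAP. No analysis, sample size or visit schedule needs to change for the wording itself. Any added follow-up work depends on the scope the sponsor selects.

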#### **8.3.4 Regulatory reporting requirements for SAEs**

Prompt notification by the Investigator to the Sponsor of a SAE is essential so that legal obligations and ethical responsibilities towards the safety of study participants and the safety of a study treatment under clinical investigation are met.

The Sponsor has a legal responsibility to notify both the local regulatory authority and other regulatory agencies about the safety of a study treatment under clinical investigation. The Sponsor will comply with country-specific regulatory requirements relating to safety reporting to the regulatory authority, IEC, and Investigators.

Investigator safety reports must be prepared for suspected unexpected serious adverse reactions (SUSAR) according to local regulatory requirements and Sponsor policy and forwarded to Investigators as necessary.

An Investigator who receives an Investigator safety report describing a SAE or other specific safety information (eg, summary or listing of SAEs) from the Sponsor will review and then file it along with the IB and will notify the IEC, if appropriate according to local requirements.

#### **8.3.5 Pregnancy**

Details of all pregnancies in female study participants and, if indicated, female partners of male study participants will be collected after the start of the inhouse treatment period and for at least 20 weeks after the administration of IMP (anticipated 5 half-lives).

If a pregnancy is reported, the Investigator must immediately inform the Sponsor within 24 hours of learning of the pregnancy and should follow the procedures outlined in Appendix 4 (Section 10.4).

The study participant should be withdrawn from the study as soon as pregnancy is known (by positive pregnancy test), and the following should be completed:

- The study participant should return for an early discontinuation visit.
- A Safety Follow-Up Visit should be scheduled 20 weeks after the date of administration of the study participant's IMP.

Abnormal pregnancy outcomes (eg, spontaneous abortion, fetal death, stillbirth, congenital anomalies, and ectopic pregnancy) are considered SAEs.

#### **8.3.6 Adverse events of special interest**

An AE of special interest is any AE that a regulatory authority has mandated be reported on an expedited basis, regardless of the seriousness, expectedness, or relatedness of the AE to the administration of a UCB product/compound.

For bimekizumab, the following event requires immediate reporting (within 24 hours, regardless of seriousness) to UCB:

- Hy's Law
  - Potential Hy's Law, defined as  $\geq 3 \times \text{ULN}$  ALT or AST with coexisting  $\geq 2 \times \text{ULN}$  total bilirubin in the absence of  $\geq 2 \times \text{ULN}$  ALP, with no alternative explanation for the biochemical abnormality (ie, without waiting for any additional etiologic investigations to have been concluded). Follow-up information should be reported if an alternative etiology is identified during investigation and monitoring of the study participant.

#### **8.3.6.1 Other safety topics of interest**

Prespecified safety topics of interest for the study are: infections (serious, opportunistic, fungal and TB), neutropenia, hypersensitivity, suicidal ideation and behavior, depression, major cardiovascular events, liver function test changes/enzyme elevations, malignancies, and inflammatory bowel diseases (with gastroenterology referral, as appropriate).

This is based on findings from the IMP clinical program to date, potential risks generally associated with biologic immunomodulators, or findings from other medicines with a related mechanism of action. There are no specific AE reporting requirements for these topics; however, special monitoring, additional data collection activities, and/or enhanced signal detection activities (within UCB) are in place.

#### **8.3.7 Medical device– AEs (ADEs, UADEs, SAEs, and USADEs) and device presentation deficiencies**

Medical device presentations are being provided for use in this study. In order to fulfill regulatory reporting obligations worldwide, the Investigator is responsible for the detection and documentation of events meeting the definitions of incident or malfunction that occur during the study with such device presentations.

Adverse events will be reported according to the ISO 14155:2011, while recognizing and following requirements including reporting timelines specified in other specific laws, regulations, directives, standards and/or guidelines as appropriate and as required by the countries in which the clinical investigation is conducted.

The definition of a Medical Device Deficiency can be found in Appendix 7 (Section 10.7).

Note: Events fulfilling the definition of an AE/SAE will also follow the processes outlined in Section 8.3.3 and Appendix 3 (Section 10.3).

##### **8.3.7.1 Time period for detecting medical device presentation deficiencies**

Medical device presentation deficiencies or malfunctions of the device presentation that result in reportable events will be detected, documented, and reported on the date of IMP administration when the medical device presentation is used.

The method of documenting Medical Device Deficiency is provided in Appendix 7.

### **8.3.7.2 Follow-up of medical device presentation deficiencies**

Follow-up applies to all study participants, including those who discontinue the study.

The Investigator is responsible for ensuring that follow up includes any supplemental investigations as indicated to elucidate the nature and/or causality of the deficiency.

New or updated information will be recorded on the originally completed form with all changes signed and dated by the Investigator.

### **8.3.7.3 Prompt reporting of medical device presentation deficiencies to the Sponsor**

Device presentation deficiencies will be reported to the Sponsor within 24 hours after the Investigator determines that the event meets the protocol definition of a medical device presentation deficiency.

The Adverse Event and Device Deficiency Report Form will be sent electronically to the Sponsor. The Sponsor will be the contact for the receipt of medical device deficiency reports.

### **8.3.7.4 Regulatory reporting requirements for medical device presentation deficiencies**

The Investigator will promptly report all device deficiencies occurring with any medical device presentation used in the study in order for the Sponsor to fulfill the legal responsibility to notify appropriate regulatory authorities and other entities about certain safety information relating to medical device presentations being used in clinical studies.

The Investigator, or responsible person according to local requirements (eg, the head of the medical institution), will comply with the applicable local regulatory requirements relating to the reporting of device deficiencies to the IEC.

## **8.4 Safety signal detection**

Selected data from this study will be reviewed periodically to detect as early as possible any safety concern(s) related to the IMP so that Investigators, clinical study participants, regulatory authorities, and IECs will be informed appropriately and as early as possible.

The UCB Study Physician or medically qualified designee/equivalent will conduct an ongoing review of SAEs and perform ongoing SAE reconciliations in collaboration with the Patient Safety (PS) representative.

As appropriate for the stage of development and accumulated experience with the IMP, medically qualified personnel at UCB may identify additional safety measures (eg, AEs, vital signs, laboratory, or ECG results) for which data will be periodically reviewed during the course of the study.

## 8.5 Treatment of overdose

For this study, any dose of bimekizumab greater than a single-dose administration of 320mg will be considered an overdose. Overdose events are only considered AEs or SAEs if there are associated clinical signs and symptoms.

## 8.6 Pharmacokinetics

Whole blood samples will be collected for measurement of plasma concentrations of bimekizumab as specified in the schedule of activities (Section 1.3). Instructions for the collection and handling of biological samples will be provided by the Sponsor. The actual date and time (24-hour clock time) of each sample will be recorded. The overall blood volume to be drawn from each study participant participating in the study will not exceed 450mL, ie, the amount of a blood donation.

Samples will be used to evaluate the PK of bimekizumab.

Genetic analyses will not be performed on these blood samples. Study participant confidentiality will be maintained. At visits during which blood samples for the determination of multiple aspects of bimekizumab will be taken, one sample of sufficient volume can be used.

All PK samples should be drawn from study participants after the ECG has been recorded and the vital signs, including BP, have been measured. The following PK parameters will be derived from the plasma concentrations of bimekizumab:

- Area under the plasma concentration-time curve from time zero to infinity (AUC)
- Area under the plasma concentration-time curve from time zero to the last quantifiable concentration (AUC[0-t])
- Maximum observed plasma drug concentration (Cmax)
- Time of occurrence of Cmax (tmax)
- Apparent terminal half-life (t1/2)
- Apparent total body clearance (CL/F) after subcutaneous administration , calculated as dose/AUC
- Apparent volume of distribution (Vz/F), calculated as CL/λz
- Percentage of the AUC extrapolated from Clast (%AUCex)

All PK analyses will be performed under the supervision of the Quantitative Clinical Pharmacology Department, UCB using validated software (Phoenix 64, Pharsight, a Certara Company, USA).

Any changes in the timing or addition of time points for any planned study assessments must be documented and approved by the relevant study team member and then archived in the Sponsor and site study files, but will not constitute a protocol amendment. The IEC will be informed of any safety issues that require alteration of the safety monitoring scheme or amendment of the ICF.

Pharmacokinetic samples for concentration measurement of bimekizumab may be stored for a maximum of 5 years (or according to local regulations) following the last study participant's last visit at a facility selected by the Sponsor.

## **8.7           Genetics**

Genetics are not evaluated in this study.

## **8.8           Pharmacodynamics**

Pharmacodynamic parameters are not evaluated in this study.

## **8.9           Biomarkers**

Biomarkers are not evaluated in this study.

## **8.10          Immunogenicity assessments**

Antibodies to bimekizumab will be evaluated in plasma samples collected from all study participants according to the schedule of activities (Section 1.3). Additionally, plasma samples should also be collected at the final visit from study participants who were withdrawn from the study. These samples will be tested by the Sponsor or Sponsor's designee.

Plasma samples will be screened for antibodies binding to bimekizumab and the titer of confirmed positive samples will be reported. Other analyses may be performed to verify the stability of antibodies to bimekizumab and/or further characterize the immunogenicity of bimekizumab.

The detection and characterization of antibodies to bimekizumab will be performed using a validated assay method by or under the supervision of the Sponsor. Anti-drug-antibodies will be measured using a three-tiered assay approach: screening assay, confirmatory assay, and titration assay. Samples may be stored for a maximum of 5 years (or according to local regulations) following the last study participant's last visit for the study at a facility selected by the Sponsor to enable further analysis of immune responses to bimekizumab.

